Bromhexine, a well known pharmacological drug, is an alkaloid derived from Adhatoda vasca used as a secretolytic expectorant for the treatment of respiratory diseases with excessive or viscous mucus. Bromhexine stimulates the activity of the ciliated epithelium, enhances lysosomal activity and causes hydrolytic depolymerization of mucous protein fibers [Bhagat A, Rachana R. Bromhexine: A Comprehensive Review. Int J Bio Med Res. 2018; 9 (3): 6455-9]. The concentration of Bromhexine in the pulmonary parenchyma two hours after administration is 2.4-5.9 times higher than in the blood plasma. The drug demonstrates first-order pharmacokinetics and is almost completely metabolized to a variety of hydroxylated metabolites; the most famous of these is Ambroxol, also available as a licensed mucolytic drug.

Like Camostat, Bromhexine inhibits the activity of TMPRSS2, thus preventing the SARS-CoV-2 virus from entering the cell. Bromhexine blocks the ability of TMPRSS2 to activate the tissue zymogen precursor, plasminogen activator in vitro [Lucas JM, Heinlein C, Kim T, Hernandez SA, Malik MS, True LD et al. The Androgen-Regulated Protease TMPRSS2 Activates a Proteolytic Cascade Involving Components of the Tumor Microenvironment and Promotes Prostate Cancer Metastasis. Cancer Discovery. 2014; 4: 1310-25].

It is important to note that only minor side effects of Bromhexine have been described, such as nausea (a common effect), rash, bronchospasm, vomiting, diarrhea, and fever (noted as a rare effect). Severe complications, such as Stevens-Johnson syndrome, or toxic epidermal necrolysis, possibly associated with the metabolite Ambroxol, are casuistic (no more than 0.16 cases per million patients).

There are currently no results of prospective studies of the use of Bromhexine hydrochloride as a preventive measure. There is one known study planned in China (Evaluating the Efficacy and Safety of Bromhexine Hydrochloride Tablets Combined With Standard Treatment / Standard Treatment in Patients With Suspected and Mild Novel Coronavirus Pneumonia (COVID-19) clinicaltrials.gov: NCT04273763; sample of 60 patients, start date studies 02/16/2020 Two prospective placebo-controlled studies are also known to study the effect of

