Camostat on reducing the severity of the incidence of COVID19: The Effect of Camostat Mesylate on COVID-19 Infection in Ambulatory Patients: An Investigator-Initiated Randomized, Placebo-Controlled, Phase IIa Trial, clinicaltrials.gov: NCT04353284, sample of 114 patients, study start date 04/30/2020 (Yale University, USA); The Impact of Camostat Mesilate on COVID-19 Infection: An Investigator-initiated Randomized, Placebo-controlled, Phase IIa Trial; clinicaltrials.gov: NCT04321096, sample of 180 patients, study start date - 03/31/2020 (Dani me, 9 participating centers).

We suggest, that when SARS-CoV-2 has already entered the cells, the effect of Bromhexine hydrochloride therapy will be low or insufficient. About 20-30% of medical personnel are infected with SARS-Cov-2. At the same time, there are similar data on the potential effectiveness of Bromhexine hydrochloride in the prevention of a new infection in risk groups from several independent groups of authors. According to data from personal communication with specialists in Germany, there were no cases of infection among those who took the drug prophylactically [Department of Anesthesiology, Intensive Care, Pain Management and Palliative Care, Marienkrankenhaus, Soest, Germany]. It can be assumed that there is a preventive effect of taking Bromhexine among medical personnel to reduce the risk of infection and COVID 19 disease, despite the use of personal protective equipment.

2. Purpose

To evaluate the efficacy and safety of oral administration of Bromhexine hydrochloride for the prevention of SARS-CoV-2 infection and COVID-19 disease in medical personnel managing patients with COVID-19

3. Study type

Prospective randomized open-label study with a control group, which assesses the superiority of prophylactic therapy

4. Inclusion criteria

- 1. Age \geq 18 years;
- 2. Negative test (PCR) for SARS-CoV-2 infection;
- 3. Absence of clinical manifestations of a respiratory infection;
- 4. Presumptive management of patients with laboratory and/or clinically confirmed COVID-19;
- 5. Signed informed consent to participate in the study.

5. Exclusion criteria

- 1. Intolerance to Bromhexine hydrochloride;
- 2. Work outside of contact with SARS-CoV-2 infection;
- 3. Pregnancy (positive laboratory test for pregnancy or ultrasound confirmation of pregnancy) and breastfeeding period;
- 4. Other circumstances that the researcher considers inappropriate to participate in this study.

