- 5. Peptic ulcer or duodenal ulcer, incl. in anamnesis

6. Documented contact with a SARS-CoV-2 carrier or a COVID-19 patient within 14 days prior to randomization

6. Drop out criteria

1. Failure to comply with the rules for the use of personal protective equipment when working with SARS-CoV-2 infection (the rules for the use of PPE in accordance with the recommendations of the Ministry of Health of Russia and internal orders of the General Director of the V.A. research; control of the use of PPE - independent);

2. Any acute illness not associated with SARS-CoV-2 that occurred during the study period

[figure not shown]
7. Study design

[figure not shown]
This is single-center study. Location of the study center:

Almazov National Medical Research Centre; [name]

Study design is present on Figure 1.

• When COVID-19 is expected clinically or SARS-CoV-2 infection is verified with a positive PCR test, the endpoint is reached and the drug may be canceled;

• However, the drug can be continued at the request of the participant for mild and moderate forms of the disease, since, theoretically, a decrease in viral load is possible; patients with continued therapy will continue to be followed, but outside the study protocol.

The same test systems for PCR (SARS-CoV-2 infection) will be used during the study.

8. Study endpoints

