8.1 Primary endpoint

• Combined endpoint: a positive PCR swab test to SARS-CoV-a2 and/or clinically suspected COVID-19 at 4 weeks and/or after 14 days after the last contact with a SARS-CoV-2 positive person

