8.3 Methods for assessing primary and secondary endpoints

1. Clinical assessment of study participants for the presence of symptoms of respiratory infection

- 2. Laboratory diagnostics of the presence of SARS-CoV-2: swab PCR test;
- 3. Chest computed tomography, pulse oximetry to assess the severity of the disease;

4. Laboratory diagnostics of SARS-CoV-2 infection: plasma IgG;

5. Laboratory diagnostics of the severity of COVID-19: clinical blood test with leukocyte count, C-reactive protein, D-dimer, ALT, AST, bilirubin fraction; creatinine, urea, protein fractions; amylase; glucose;

6. The need for oxygen support and its type in the treatment of COVID-19; the duration of the need for oxygen therapy; duration of mechanical ventilation.

7. Working hours (hours) with patients with confirmed / suspected SARS-CoV-2 infection;

8. Additional observation of all study participants up to 8 weeks from the date of randomization.

Methodology for calculating the time of work with SARS-CoV-2 infection

1. Units of time calculation - hours;

2. Separately taken into account: a) the time of work in the therapeutic department, including the emergency room where patients with suspected / confirmed SARS-CoV-2 infection are located; b) the time of work in the intensive care unit, where patients with suspected / confirmed SARS-CoV-2 infection are located; c) the time of work in a "clean" area, outside the presence of patients with suspected / confirmed SARS-CoV-2 infection;

3. Working hours in the hospital without personal protective equipment in accordance with the regulations of Almazov National Medical Research Centre.

9. Randomization and sample size estimation

Randomization method: 1:1, allocation by minimization method to the preventive therapy group with Bromhexine hydrochloride and to the control group, taking into account the following factors: age (ranges 18-45, 45-64, 65-74, 75-79); type of contact with SARS-CoV-2 infection: ("red zone"; "green" zone); taking hydroxychloroquine to prevent COVID-19.

• "Red" zone: the closest and longest contact with SARS-CoV-2 infection associated with an infected aerosol (work in intensive care units and intensive care units; in operating and intervention laboratories; work with biological material of infected patients);

• Green Zone: work outside direct contact with patients with confirmed / suspected SARS-CoV-2 infection.

Known statistics:

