• The incidence rate of medical personnel working with SARS-CoV-2 infection: ranges between 20 and 50% (https://www.cdc.gov/mmwr/volumes/69/wr/mm6915e6.htm?deliveryName=USCDC_425-DM25898);

• Frequency of serious side effects of bromhexine hydrochloride: no more than 0.16 cases per million patients (Ambroxol and bromhexine containing medicinal products. EMA / PRAC / 800767/2015, 10/09/2015);

Estimated effect of preventive therapy:

Empirically, it is suggested that prophylactic drug administration can reduce the incidence of the primary endpoint by 20%.

Calculation of the study sample size:

• Power: 80%

• Confidence level - alpha error: 5%

• The incidence of the primary endpoint in the control group is estimated 30%; the incidence of the primary endpoint in the study group is estimated 10%;

• Thus, the target sample size: 118 people (59 subjects in each group)

• Estimated dropout rate from study protocol (dropout after randomization, non-SARS-CoV-2 incidence) 15%; thus, the required number of participants in the study will be 139 people;

10. Bromhexine hydrochloride dosing and administration rules

The drug is administered orally, after meals, without chewing, with plenty of liquid: 3 times a day, 8 mg.

In case of impaired renal function (creatinine clearance <30 ml / min / 1.73 m2) and / or liver insufficiency (an increase in the level of hepatic transaminases by 2 or more times), the drug should be discontinued in this study.

11. Study timeline

Evaluations	0	7 days	14 days	21 days	28 days	5-8 weeks		
Test (PCR) SARS- CoV-2	+	+	+	+	+	+		
Enzyme immunoassay - IgG to SARS- CoV-2	+*							
Clinical follow-up, daily	+	+	+	+	+	+		
Bromhexine hydrochloride administration, daily (8 mg 3 times a day)	+	+	+	+	+	+		
Individual protective equipment; daily	+	+	+	+	+	+		
Concomitant pharmacological treatment record	+	+	+	+	+	+		
Participant's questionnaire maintaining	+	+	+	+	+	+		
Laboratory diagnostics when SARS-CoV-2 is expected			When indicated					
Chest computed tomography when SARS-CoV-2 infection is expected				When indica	ted			

Table 1. Schedule of evaluations and prophylactic measures

*Plasma biobanking with subsequent IgG analysis when it is possible

12. Subject exclusion

Participants in the study can leave at any time, for any reason, without any consequences. A participant might be excluded from the study for a medical emergency.

Study participant specific withdrawal criteria:

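### Clinically suspected COVID-19 without PCR confirmation counts as a primary event in an open-label trial, so suspected-only events can produce or mask superiority with no difference in infection

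*Combined protocol and SAP*

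**What the plan says.** - **Endpoint.** Section 8.1 counts "a positive PCR swab test to SARS-CoV-a2 and/or clinically suspected COVID-19 at 4 weeks"; a second time point, 14 days after last contact, is also allowed. Section 7 states the trigger: "When COVID-19 is expected clinically or SARS-CoV-2 infection is verified with a positive PCR test, the endpoint is reached". Neither place asks for PCR confirmation of a suspected case.
- **Assessment.** The first method in section 8.3 is "Clinical assessment of study participants for the presence of symptoms of respiratory infection". Clinical suspicion has no case definition. CT and pulse oximetry are listed there for severity. Section 11 schedules laboratory work and CT when indicated, but no rule says that their results confirm or cancel a suspected event.
- **Design.** Section 3: "Prospective randomized open-label study with a control group, which assesses the superiority of prophylactic therapy". No placebo and no blinded assessment of events are described.
- **Drug.** Section 1 describes bromhexine as "used as a secretolytic expectorant for the treatment of respiratory diseases with excessive or viscous mucus". It also lists bronchospasm and fever among the side effects.
- **Secondary endpoints.** Section 8.2 has two times to event that involve PCR, the number of symptomatic infections, the number of cases by severity, and side effects. They are not ranked. The proportion with PCR-confirmed infection is not among them, and nothing ties the trial's conclusion to PCR.
- **Follow-up.** Section 11 schedules PCR at days 0, 7, 14, 21 and 28 and in weeks 5–8, and section 8.3 item 8 foresees observing everyone to 8 weeks. However, section 12 makes suspected or confirmed infection a ground for withdrawal, and section 7 places those who continue the drug after an event outside the protocol.

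**The concern.** Section 2 aims to prevent both SARS-CoV-2 infection and COVID-19 disease. A respiratory illness that never yields a positive swab has not been shown to be either, yet it carries the same weight in the primary analysis as a confirmed infection.

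That component can differ between arms for reasons unrelated to the virus. The drug may change respiratory symptoms, in either direction. Participants and clinicians who know the allocation may also report symptoms, or suspect COVID-19, more readily in one arm. If suspected-only events fall on bromhexine, the composite can be significant with no infection prevented, and could be reported as prevention of infection. If they are unchanged or rise on bromhexine, a real effect on infection is diluted. Nothing in the planned reporting would let a reader tell these cases apart.

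**Working it through.** **1. The plan's own figure.** Inputs from section 9: control 30%, bromhexine 10%, alpha 5%, power 80%, 1:1 allocation. Sidedness and test are not stated; I take two-sided. With unpooled variance:

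n per arm = [p₁(1−p₁) + p₂(1−p₂)] × (1.960 + 0.842)² / (p₁−p₂)² = (0.21 + 0.09) × 7.849 / 0.04 = 58.87, hence 59 per arm and 118 in total. With 15% dropout, 118/0.85 = 138.8, hence 139. Both figures reproduce, so the arithmetic is sound. The question is what the 30% v 10% difference measures.

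**2. Superiority with no difference in infection.** The split of the 30% control rate is not in the documents, so it is assumed. Let *s* be the suspected-only part in percentage points and *r* the fraction by which it is lower on bromhexine, for whatever reason. PCR-positive rates are equal, so the bromhexine composite is 30 − *s·r*. The probability of a significant result favouring bromhexine comes from exact binomial enumeration at 59 per arm (two-sided 5% chi-square without continuity correction).

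| *s* (points) | *r* | Control v bromhexine | Chance of significant superiority |
|---|---|---|---|
| any | 0 | 30% v 30% | 2.6% |
| 5 | 20% | 30% v 29% | 3.4% |
| 10 | 20% | 30% v 28% | 4.4% |
| 10 | 50% | 30% v 25% | 9.0% |
| 10 | 80% | 30% v 22% | 17.0% |
| 15 | 80% | 30% v 18% | 34.0% |

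**3. The other direction.** Suppose instead that bromhexine cuts infection by two thirds, the planned relative effect ((30−10)/30), and leaves suspected-only illness unchanged.
- *s* = 5: bromhexine composite = 25/3 + 5 = 13.3%, power 61%.
- *s* = 10: bromhexine composite = 20/3 + 10 = 16.7%, power 41%.

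The same enumeration gives 80.5% for the planned 30% v 10%. Steps 2 and 3 assume different effects on suspected-only illness. They are alternatives and should not be combined.

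**4. Which claim rule controls the error.** I compared two conditions for claiming prevention of infection, each added to a significant composite, by simulation with equal PCR-positive rates.
- *PCR difference merely favours bromhexine in sign.* In the last three rows of the table, false claims fall from 9.0% to 8.8–8.9%, from 17.0% to 16.4%, and from 34.0% to 28.0%. About 98%, 96% (16.4/17.0) and 82% (28.0/34.0) of them remain. The PCR events are part of the composite, so when the composite is significant their difference usually points the same way.
- *95% CI for the PCR risk difference excludes zero in favour of bromhexine.* False claims stay at about 2–3% in the same scenarios, because with equal infection rates the interval itself errs in that direction only about 2.5% of the time.

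**5. Cost in power.** At 20% v 6.7% PCR-positive, the PCR comparison at 59 per arm has 57% power (pooled normal formula) or 59% (exact enumeration). The claim also needs a significant composite, so its power is no higher than this.

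**The case against.** **The drug mechanism.** A reader might infer that bromhexine's mucolytic action will itself lower the composite, and would do so even under a strict case definition with blinded assessors. The documents do not support that. Section 1 describes use in disease with excessive or viscous mucus. It does not say that a secretolytic prevents an illness from being suspected as COVID-19. Its side-effect list includes bronchospasm and fever, which could raise suspicion on the drug. A definition requiring PCR or other objective confirmation would close or narrow the route. Open-label reporting acts through the same component and may matter as much. The point therefore has to be made without a fixed mechanism or direction.

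**The size.** Both the suspected-only share and its reduction are assumed, and reductions of 50–80% have no basis in the documents. This stands. With a 20% reduction the inflation is slight (3.4–4.4%).

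**Existing safeguards.** Three deserve credit. A clinical component is legitimate, because the purpose includes disease. Section 8.2 has PCR-based secondaries. Section 6 drops participants with acute illness not associated with SARS-CoV-2, which could remove some diluting events. None settles the matter: the secondaries govern no claim, and under open-label conditions a PCR-negative illness may be judged either a primary event or a dropout.

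**The swabs.** A reader might infer that the scheduled swabs already give a measure of infection independent of symptoms. Sections 7 and 12 do not secure that. A participant suspected on symptoms may be withdrawn before the remaining swabs, so PCR ascertainment could depend on symptoms and on arm.

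**Conclusion.** The concern holds in this limited form: the design allows suspected-only events to produce or mask superiority without any difference in infection, and the plan has no analysis or claim rule that would reveal it. The documents do not show that this will happen, or in which direction.

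Under the stated assumptions (59 per arm, 30% control composite, equal PCR-positive rates), the chance of false superiority in the scenarios with 10 or 15 suspected-only points is 4%, 9%, 17% or 34%, against 2.6% under no difference. It stays close to nominal if suspected-only events are few or differ little between arms. If a true two-thirds reduction in infection is diluted by 5 or 10 points of unaffected suspected illness, power falls to 61% or 41%.

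The sample size is not miscalculated and the composite need not be abandoned. The sponsor should make this change, because the remedy is cheap and it protects the trial's main claim.

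**What to change.** Keep the composite and the sample size, and amend four places.

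1. **Section 8.2.** Add as first-ranked secondary the proportion of all randomised participants with PCR-confirmed SARS-CoV-2 by day 28 from the scheduled swabs, with risk difference and 95% CI. State how missing swabs are counted.
2. **Reporting.** Tabulate primary events by arm as PCR-positive or suspected without positive PCR.
3. **Claim rule.** State that the trial will claim prevention of SARS-CoV-2 infection only if the composite is significant and the 95% CI for the PCR-confirmed risk difference excludes zero in favour of bromhexine. Otherwise the conclusion is limited to fewer PCR-positive or clinically suspected illnesses. Agreement in sign is not enough.
4. **Sections 7, 8.3 and 12.** Reconcile withdrawal on suspected infection, and follow-up outside the protocol, with observation of all participants to 8 weeks, so that scheduled swabs and data collection continue after a suspected-only event. This concerns data collection only; whether the drug is continued is a separate matter.

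Cost: a few sentences and one table, plus the effort of obtaining swabs already scheduled from participants who would otherwise have left. The power of the primary is unchanged. The infection-specific claim has at most about 57–59% power at 20% v 6.7%, and the protocol should say so. These steps limit what can be claimed; they do not recover power lost to dilution.

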8.2 Secondary endpoints

- The time to the onset of clinical symptoms of a respiratory infection with positive SARS-CoV-2 PCR from the moment of the first contact with COVID-19;
- Time to a positive swab PCR SARS-CoV-2;
- Number of symptomatic cases of SARS-CoV-2 infection in both study groups;
- The number of mild, moderate and severe forms of COVID-19;
- The presence and type of side effects of Bromhexine hydrochloride

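### Time to symptomatic infection is counted from first contact with COVID-19, an undefined event that usually follows randomisation and may be missing; it should be counted from randomisation

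*Combined protocol and SAP*

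**What the plan says.** The first secondary endpoint in section 8.2 is the time to a symptomatic respiratory infection with a positive PCR, counted "from the moment of the first contact with COVID-19". The next one, "Time to a positive swab PCR SARS-CoV-2", names no starting point. The readable text does not define first contact. It gives no rule for a participant who has no contact or who falls ill before any recorded contact. The contents list shows no statistical analysis section, and no method is given for either endpoint.

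Other passages bear on where the clock can start:

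- Section 4, inclusion 4, expects COVID-19 work to follow entry: "Presumptive management of patients with laboratory and/or clinically confirmed COVID-19".
- Section 5, exclusion 2, bars "Work outside of contact with SARS-CoV-2 infection".
- Section 5, exclusion 6, bars "Documented contact with a SARS-CoV-2 carrier or a COVID-19 patient within 14 days prior to randomization".
- Section 9 makes type of contact a minimisation factor, and one level is "Green Zone: work outside direct contact with patients with confirmed / suspected SARS-CoV-2 infection".
- Section 3 describes a "Prospective randomized open-label study with a control group, which assesses the superiority of prophylactic therapy".
- Section 8.3, item 8, sets follow-up by the randomisation date: "Additional observation of all study participants up to 8 weeks from the date of randomization". The schedule in section 11 likewise starts study drug and PCR testing at day 0.

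**The concern.** In a randomised time-to-event comparison the clock should start at a point that everyone has and that allocation cannot influence. First contact meets neither condition. For most participants it happens after allocation, in a trial where staff and managers know who takes the drug. If working patterns or contact recording then differ by arm, the measured intervals differ for reasons unrelated to any delay in onset. Participants without a recorded contact have no interval, so their events drop out of this endpoint. What is at stake is the interpretation of one secondary endpoint, and by extension of the PCR endpoint beside it if a reader assumes the same origin.

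**Working it through.** **1. Where the origin can fall.**

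| Position of first contact | Basis in the protocol | Consequence |
|---|---|---|
| After randomisation | Inclusion 4 (contact expected) with exclusion 6 | Usual case; the origin is a post-allocation event |
| Within 14 days before | Barred by exclusion 6 if documented | Only undocumented contact |
| More than 14 days before | Not barred | Residual case; the interval includes time before allocation and off study drug |
| None, or none recorded | Green-zone level in section 9, which conflicts with exclusion 2 | No interval can be computed |

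Two invented participants show the effect on recorded times. Contact on day 10 and symptoms on day 20 give 20 − 10 = 10 days. Contact 40 days before randomisation and symptoms on day 10 give 10 − (−40) = 50 days, although this person fell ill 10 days earlier on the trial clock. This shows scatter between individuals, not bias between arms.

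**2. What counts as contact.** Exclusion 6 counts contact with a carrier or a patient, section 8.1 refers to a person who tested positive, and section 8.2 refers only to the disease. Whether an infected colleague counts decides whether some cases have a start time. Section 8.3, item 7, records hours worked with patients, not a date of first contact.

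**3. The plan's own figure.** Section 9 gives 30% v 10%, power 80% and alpha 5% (two-sided reproduces the stated number). With unpooled variance:

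n = (1.960 + 0.842)² × (0.30×0.70 + 0.10×0.90) / 0.20² = 7.85 × 0.30 / 0.04 = 58.9, so 59 per group and 118 in all. With 15% dropout, 118 / 0.85 = 138.8, so 139. The figure reproduces. It belongs to the binary primary endpoint and does not depend on the origin discussed here.

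**4. Simulation of the two clocks.** From section 9: N = 118 and 28-day risks of 30% and 10%, a hazard ratio of ln(0.90)/ln(0.70) = 0.295. These are primary-endpoint risks, so the contrast between clocks matters more than the absolute power. Assumed, because the documents give no distribution: first contact uniform on days 0–10; prior contact, where present, 15–42 days before randomisation; infection risk not tied to first contact. People without contact, or infected before it, have no usable time on the contact clock. Log-rank test, 2000 runs per row; each cell is randomisation clock / contact clock.

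| Scenario | Rejection, no drug effect | Power, 30% v 10% | Mean events used, 30% v 10% |
|---|---|---|---|
| All have contact on days 0–10 | 0.048 / 0.052 | 0.796 / 0.709 | 23.6 / 18.9 |
| 20% with prior contact | 0.050 / 0.052 | 0.804 / 0.698 | 23.7 / 19.9 |
| 30% never | 0.063 / 0.056 | 0.785 / 0.525 | 23.5 / 13.3 |
| 20% prior, 30% never | 0.044 / 0.050 | 0.792 / 0.540 | 23.6 / 14.1 |
| Contact 5 days later in drug arm, constant risk | 0.048 / 0.044 | 0.800 / 0.626 | 23.8 / 18.0 |
| Contact 5 days later in drug arm, rising risk | 0.046 / 0.117 | 0.786 / 0.462 | 23.7 / 21.9 |
| Contact 10 days later in drug arm, rising risk | 0.050 / 0.262 | 0.793 / 0.180 | 23.6 / 20.9 |

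The simulation standard error at 5% is √(0.05×0.95/2000) = 0.005. With timing unrelated to arm, the contact clock keeps its error rate but loses 1 − 18.9/23.6 = 20% of events when everyone has contact, and 1 − 13.3/23.5 = 43% when 30% never do. Its error rate rises only in the rows where timing differs by arm and risk also changes over time.

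**The case against.** A reader might infer that this endpoint cannot give a valid comparison of onset times. The documents do not support that. If contact timing is unrelated to arm, type I error on the contact clock is 0.050–0.056. Nothing in the protocol shows a difference by arm, and type of contact is a minimisation factor, although that balances the zone at entry and not the later timing of contact. Time from exposure is also a reasonable question in prophylaxis.

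The bias argument also depends on the model. Suppose infection is possible only after contact, at constant risk (30% over 28 days), with no drug effect and contact 5 or 10 days later in one arm. The randomisation clock then rejects in about 0.1 and 0.3 of trials at 28 days (0.08 and 0.16 at 56 days), while the contact clock stays at 0.04–0.05. In that model, if everyone has contact, no events are lost either. This stands: the simulations show vulnerability under particular assumptions, not a proven defect. It does not rescue the stated origin. If allocation changes when staff meet patients, the randomisation clock still answers a defined question, the effect of allocation, though it cannot separate the drug from behaviour. The contact clock can separate them only if contact is defined, recorded completely and alike in both arms, and always precedes infection. The plan secures none of these.

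Three other strong readings also fail. A clock that starts before allocation is a residual case because of exclusion 6. That green-zone staff never have contact does not follow, since exclusion 2 bars work outside contact and contact with a carrier may count; the documents give no green-zone share. And an event without a contact date is lost only to this endpoint: the primary endpoint, the count of symptomatic cases and the time to positive PCR can still capture it.

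**Conclusion.** The point holds for one secondary endpoint, as an improvement that should be made. The stated origin is undefined, usually follows randomisation and may be missing, so the endpoint does not compare everyone randomised and is open to bias after open-label allocation. If infections can occur before or without a recorded contact, power falls from about 0.80 to about 0.70, or to about 0.53–0.54 with 30% never in contact. If contact also comes later in one arm while risk rises, type I error was 0.12 (5 days) or 0.26 (10 days). The contact distribution, the prior-contact and never-contact shares and the shift by arm are all assumptions. The documents do not show that bias occurs. The primary endpoint and the 118/139 sample size are unaffected.

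**What to change.** In section 8.2, replace the first-contact origin with randomisation, and state the same origin for the time to a positive PCR. Add that both endpoints include all randomised participants and are censored at 8 weeks or at the last assessment, whichever comes first. The cost is a short edit: the randomisation date is known for everyone and no new data are needed. A small downside is that low-risk time before first contact is included, which may dilute the contrast slightly.

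If time from exposure remains of interest, keep it as a supplementary analysis. Define first contact, including whether an infected colleague counts, add its date to the data collected under section 8.3, and say how participants with no contact, or with onset before contact, are handled. Exclusion 2 and the green-zone level in section 9 also need to be reconciled.
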